2.1.2. FGFR Activating Mutations

FGFR gene mutations are widespread in tumors. It was reported that urothelial bladder carcinoma has the most established association with altered FGFR signaling, with up to 80% of poorly differentiated tumors harboring FGFR mutations^[9]. The most common activating mutations affect either the extracellular (R248C, S249C) or the transmembrane (G370C, S371C, Y373C, G380R, A391E) domains of the protein. FGFR2 mutations have been found in 12% to 14% of endometrial cancer. And, the activating mutations of FGFR4 are found in 6% to 8% of subjects with rhabdomyosarcoma^[9].

2.1.3. FGFR gene amplification / protein overexpression

Unlike some receptor tyrosine kinases (such as c-Met), overexpression of FGFRs may lead to ligand-independent FGFR signaling and is mainly caused by gene amplifications. FGFR1 amplification has been found in approximately 7% to 20% of squamous non–small cell lung carcinoma, 18% of osteosarcoma, and 6% of small cell lung carcinoma^[9]. In breast cancer, amplification of FGFR1 have been observed in 23% of HR-positive, 27% of HER2-amplified, and 7% of triple-negative cases. FGFR2 amplification has been found in 4% of triple-negative breast cancer and 4%–9% of gastric cancers^[9]. FGFR gene amplification/protein overexpression is thought to be closely related to early tumor recurrence, efficacy prediction and prognosis, and high sensitivity to FGFR inhibitors.

2.1.4. Development status of FGFR inhibitors

The FGFR inhibitors currently under investigation mainly include small molecule FGFR tyrosine kinase inhibitors (non-selective and selective) and FGFR monoclonal antibodies.

Up to now, only one selective FGFR inhibitor- Balversa[™] erdafitinib received accelerated approval by FDA for the treatment of adult patients who had progressed during or following at least one line of prior platinum-containing chemotherapy with locally advanced or metastatic urothelial carcinoma that has susceptible FGFR3 or FGFR2 genetic alterations^[10]. The approval

was based on a single arm phase 2 study where erdafitinib was associated with an ORR of 32.2% in patients with locally advanced or metastatic urothelial carcinoma with specific FGFR alterations identified based on a clinical trial assay performed at a central lab^[10]. Erdafinitib was associated with significant toxicities in the pivotal phase 2 study with grade 3-4 adverse drug reactions in 67% of subjects, dose interruptions in 68% of patients, dose reductions in 53% of patients, and permanent discontinuations in 13% of patients^[10]. Therefore, more FGFR inhibitors with improved tolerability and/or efficacy are still needed.

Ongoing clinical research with several investigational FGFR inhibitors showed preliminary evidence of efficacy in patients with FGFR alterations across several tumor types including biliary tract cancer, urothelial cancer, lung cancer, gastrointestinal cancer, and breast cancer. For example, in the first in human (FIH) study of BGJ398, 32.9% (28/85) of patients with advanced solid tumors at the dose ≥ 100 mg had reduced tumor burden after treatment with BGJ398^[11]. Among them, the disease control rate (DCR) in patients with FGFR3-mutated bladder/urothelial cancer treated was 75%, and the DCR in patients with FGFR1-amplified sqNSCLC was 50%^[12]. In a further phase 2 study of BGJ398, the DCR was as high as 82% in patients with cholangiocarcinoma containing FGFR2 fusions^[13]. In addition, in the study of the selective FGFR inhibitor AZD4547, the DCR reached to 55.5% in patients with FGFR2-amplified gastric/esophageal cancer, and, in patients with FGFR1-amplified breast cancer, the DCR was 37.5%^[14, 15]. Previous clinical studies have indicated that the toxicity profile of non-selective FGFR inhibitors is similar to vascular endothelial growth factor receptor (VEGFR) tyrosine kinase inhibitors (TKI), whereas selective FGFR inhibitors have specific toxicity types associated with FGFR pathway inhibition. So far, the major drug-related AEs observed in the clinical studies of FGFR selective inhibitors are mostly mild to moderate and reversible, including hyperphosphatemia, nail, and mucosal disorders, fatigue, reversible RPED, etc.^[10-17], while VEGFR-related cardiovascular toxicity such as high blood pressure has not been noted. Considering the multiple physiological functions of FGFRs, the feasibility of long-term use of FGFR inhibitors in cancer patients remains to be defined.

2.2. 3D185 Overview

The 3D185 (original development code: HH185) tablets is a novel oral selective FGFR inhibitor developed by 3D Medicines and Haihe Biopharma. 3D Medicines has the rights for clinical development, production and commercialization of 3D185 for the treatment of advanced solid tumors.

The selective inhibition of FGFRs, pharmacodynamic effects, and mechanisms of actions of 3D185 have been systemically studied at molecular, cellular, and in vivo animal levels preclinically using another clinical stage FGFR selective inhibitor AZD4547 as the control. 3D185

is a potent inhibitor of FGFR1-3 and a weak inhibitor of FGFR4 and over 300 other receptor tyrosine kinases. 3D185 also showed FGFR selectivity at the cellular level.

As a selective inhibitor of FGFR1-3, 3D185 has the potential advantages of reduced toxicity, easier patient selection, and amenable to combination therapy. 3D185 has the potential to become a new effective treatment for cancer subjects.

2.2.1. Summary of 3D185 Preclinical Studies

2.2.1.1. Pharmacokinetics

The pharmacokinetics of 3D185 were studied in Sprague Dawley rats and Beagle dogs after single and multiple dose administration. The results are as shown below:

Clearance of 3D185 was low both in rats (15.0 mL/min/kg) and dogs (7.35 mL/min/kg). The steady-state volume of distribution (Vdss) was 5.70 L/kg and 5.82 L/kg in rats and dogs, respectively. Both exceed the total volume of fluid in the body, suggesting that it can be widely distributed into tissues. After intragastric administration, the absolute bioavailability of 3D185 ranged from 10% to 17% in both rats (6~24 mg/kg) and dogs (2~8 mg/kg). The exposure of individual differences was large. In the dosage range of 6-24 mg/kg (rats) and 2-8 mg/kg (dogs), the increase in AUC of 3D185 was basically proportional to the dosage. Elimination half-lives were 6.78 and 12.8 hours in rats and dogs, respectively. After continuous administration, there was no significant accumulation in the dogs.

After intragastric administration of 3D185 in rats, the concentration in most tissues was higher than plasma concentration. It was mainly distributed to the gastrointestinal (GI) tract, adrenal glands, spleen, liver, pancreas, kidneys and lung, with approximately 20 folds higher exposure than in the plasma. The exposure in brain and testis were low, which indicated low risk of bloodbrain barrier and the blood-testis barrier penetration. The maximum mean concentration in most tissues were detected at 2 to 6 hours post dose, with apparent individual variations. After 36 hours post dose, the mean concentrations were less than 15% of the maximum concentration in most tissues and organs. The blood and plasma concentration ratio were 0.95. Plasma protein binding (PPB) for 3D185 was observed to be 99.9%, 99.5%, and 99.8% in rat, dog and human plasma, respectively.

After intragastric administration of 3D185 in rats, the detected main form in the body was the parent drug. Three metabolites were detected. Speculated metabolic pathways included O-demethylation and sulfation. It was mainly excreted via feces in the unchanged form (parent drug) with a total cumulative recovery of 97.6% up to 96 hours. The detected main form in rat and dog plasma after single oral dose was the parent drug.

Parent drug was detected in the incubation system of 3D185 with human, monkey, dog, rat, and mouse hepatocytes. Major metabolic pathways in human hepatocytes included O-demethylation (M4), sulfation (M5) and glucuronidation (M6 and M7). The oxidative metabolites detected in human hepatocytes also can be found in hepatocytes of each animal species. CYP3A4 was the major CYP isoform responsible for 3D185 metabolism. In addition, CYP2C8, CYP2D6 and CYP3A5 also participated in the oxidative metabolism of 3D185.

3D185 did not appear to be an inhibitor of CYP1A2 and CYP3A4 (midazolam 1'-hydroxylation) (IC₅₀ was 100 μ M). 3D185 was a weak inhibitor of CYP2B6, CYP2C9, CYP2C19, CYP2D6 and CYP3A4 (testosterone, as substrate) (IC₅₀ ranged from 29.8 to 61.4 μ M) and a moderate inhibitor of CYP2C8 (IC₅₀ was 6.50 μ M). 3D185 did not show potential to cause drug -drug interactions due to induction of CYP1A2, CYP2B6, and CYP3A4. 3D185 has low permeability and may have efflux transporters involved in the transport of 3D185 on Caco-2 cells. Please refer to IB for the results of non-clinical pharmacokinetics and product metabolism studies of 3D185.

2.2.1.2. Pharmacodynamics and antitumor activity

3D185 exhibited potent inhibition of FGFR1, FGFR2 and FGFR3 in vitro, with IC₅₀ values of 0.5 ± 0.1 nM, 1.3 ± 0.1 n M, and 3.6 ± 0.5 nM, respectively, and exhibited much weaker activity against FGFR4 (IC₅₀ = 51.4 ±8.5 nM). Meanwhile, 3D185 exhibited only a marginal inhibitory effect against the activity of recombinant KDR kinase, with an IC₅₀ of 381.5 ± 10.9 nM. Moreover, the selectivity for FGFR1 over KDR was greater than 700-fold, which is much better than the selectivity exhibited by AZD4547. Interestingly, 3D185 exhibited potent inhibition of the colony stimulating factor-1 receptor (CSF-1R) tyrosine kinase, an important target in tumor-associated macrophages, suggesting that 3D185 has the potential to exert antitumor activity by synergistically targeting the tumor microenvironment. Also, the enzyme kinetic study confirmed that the compound of 3D185 is an ATP-competitive FGFR small molecule inhibitor.

Non-small cell lung cancer, gastric cancer and bladder cancer cells with different FGFR family members and different activation mechanisms (FGFR1, FGFR2 amplification, and FGFR3 mutant) were further selected to assess the cellular targeting activity of 3D185 against FGFR kinase at the cellular level. The result indicated that 3D185 significantly inhibited FGFR phosphorylation in a dose-dependent manner in the individual cancer cell lines. The phosphorylation of ERK1/2, a downstream signaling core molecule of FGFR, was also inhibited.

Abnormal activation of FGFR significantly promotes tumor cell proliferation. Thirty (30) human tumor cell lines from different family members, different activation mechanisms, and different tumor sources were selected to test the cell proliferation inhibition of 3D185. The result showed that 3D185 strongly inhibited FGFR driven cancer cell proliferation, with IC₅₀ values ranging from 0.9 to 49.8 nM, which was comparable or slightly better than AZD4547. In contrast, 3D185 was inactive against 20 additional tumor cell lines that exhibited low expression or activation of FGFR (IC₅₀ > 1 μ M or 10 μ M), further demonstrating that 3D185 is a highly potent and selective inhibitor

of FGFR. In-depth studies showed that 3D185 achieves potent antiproliferative activity by targeting FGFR signaling to induce G1/S phase arrest in cells.

In addition, 3D185 significantly inhibited the activation of bFGF/FGFR signaling pathway in primary human umbilical vein endothelial cells and FGFR-mediated endothelial cell proliferation, suggesting that it has a role in targeting FGFR pathways to antagonize angiogenesis. However, the effect of VEGF-induced KDR-mediated endothelial cell proliferation was weaker, and the IC₅₀ was nearly 200-fold different, which further showed that KDR achieved better selectivity.

Based on the good activity of 3D185 at the molecular and cellular levels, we further selected the subcutaneous xenograft model of human tumor cell lines derived from different tumor tissues driven by FGFR to investigate the in vivo antitumor effect of the drug candidate. We used a FGFR1 amplified human lung cancer NCI-H1581 model and two FGFR2 amplified models: a human gastric cancer SNU-16 model and a human colorectal cancer NCI-H716 subcutaneous xenograft model. The result indicated that 3D185 can dose-dependently inhibit the growth of subcutaneous xenografts in these three FGFR-dependent models, with NCI-H1581 being relatively more sensitive. In this model, the compounds were orally administered at 50, 25 and 12.5 mg/kg for 2 weeks, and their T/C percentages were 1.92-4.70%, 10.30-24.17% and 24.54-39.66%, respectively. It was equivalent to the same dose of the positive control compound AZD4547 (12.5 mg/kg). In FGFR2 amplified tumor models, 3D185 also showed good tumor inhibiting effect. In the human gastric cancer SNU-16 model, the percentage of T/C after 3 weeks of continuous administration in the 3D185 50 mg/kg group was 26.39-26.40%. This compound, at the dose of 25mg/kg, also significantly inhibited the growth of SNU-16 subcutaneous xenografts, with a T/C percentage of 43.83-55.41%. In the human colon cancer NCI-H716 model, after 3 weeks of continuous administration of 3D185, the T/C percentages of the 50 mg/kg and 25 mg/kg groups were 11.58-18.28% and 58.08-65.82%, respectively. Overall, 3D185 was slightly weaker in the FGFR2 amplified SNU-16 and NCI-H716 in vivo models compared to the same dose of AZD4547. Further immunohistochemical assays on Ki67 and platelet - endothelial cell adhesion molecule (CD31) in NCIH1581 and SNU16 models, indicated the in vivo antitumor activity of 3D185 involves inhibition of the downstream signaling of FGFR, with both antiproliferative and antiangiogenic consequences.

Finally, we selected FGFR-dependent human gastric cancer SNU-16 nude mouse subcutaneous xenograft model to further investigate the distribution of 3D185 in tumor tissues and plasma of tumor-bearing mice and its inhibition of FGFR signaling pathway in tumor tissues after single dose administration. The results showed that the T_{max} of 3D185 in plasma and tumor were 2-4 h and 4-8 h, respectively. Tumor exposure (AUC_{0-t}) was about 1.82- to 2.87-fold higher than plasma exposure. The elimination of 3D185 from tumor was slower than that from plasma. Dose proportional increases in plasma exposure and slightly greater than dose proportional increases in tumor exposure (AUC_{0-t}) were observed after single oral doses of 12.5 to 50 mg. The phosphorylation of ERK1/2, a key FGFR downstream signaling molecules was detected in tumor tissues, and was used to indicate inhibition of the FGFR pathway by 3D185. Significant ERK1/2

inhibition was observed in the three dose groups at 1 hour after single dose administration. After 6-8 hours, the inhibition on p-ERK was reduced in tumoral tissues with the decrease of the concentration of the compound in plasma and subcutaneous xenograft tissue. The phosphorylation levels of ERK almost fully recovered after 6 hours in low-dose group, and after 24 hours in the high-dose group. The result showed that 3D185 has a dose-dependent effect on the inhibition of FGFR pathway, and this activity also has a certain correspondence with the anti-tumor effect of 3D185 in SNU-16 model. This indicates that 3D185 significantly inhibits the growth of FGFR-dependent subcutaneous xenografts by targeted inhibition of FGFR.

3D185 selectively inhibit FGFR1-3 with selectivity over other kinases including KDR. This high selectivity may prove to be advantageous over the selective inhibitor, AZD4547 which is at a more advanced stage of clinical development. 3D185 has significant anti-tumor activity *in vitro* and *in vivo* and is highly effective in FGFR-dependent tumor models. Therefore, 3D185 has the potential to become a competitive, efficient and safe candidate new drug for tumors driven by abnormal activation of FGFRs.

2.2.1.3. Safety Pharmacology and Toxicology

• Safety Pharmacology

Respiratory system: Sprague Dawley rats were continuously monitored for 3 hours (12.5, 50, and 200 mg/kg) for at least 6 hours, and no significant drug-related changes were observed in the respiratory parameters. After a single oral gavage of Sprague Dawley rats, 3D185 12.5 mg/kg, 50 mg/kg and 200 mg/kg, no significant effect on the central nervous system was observed.

Cardiovascular system: conscious Beagle dogs were monitored for at least 24 consecutive hours after single-dose oral gavage of 3D185 (5, 20 and 60 mg/kg), and no significant drug-related change in electrocardiogram, blood pressure and body temperature were observed.

Central nervous system: Sprague Dawley rats were given 3D185 12.5 mg/kg, 50 mg/kg and 200 mg/kg in a single oral gavage, and no significant effect on the central nervous system was observed.

• Reproductive and Developmental Toxicity

After oral dose of 3D185 at 30, 10 and 3 mg/kg from GD6 to GD15 in pregnant Sprague Dawley rats, the no-observed-adverse-effect-level (NOAEL) in pregnant rats was 30 mg/kg/day. And the NOAEL for embryo-fetal development was 3 mg/kg. No significant toxicity changes were observed in the clinical symptoms, body weight and food consumption of pregnant rats in each dose group. There were no significant drug-related changes in embryonic development and fetal appearance, visceral and bone examinations in the 3 mg/kg group.

• Single-Dose Toxicity

Sprague Dawley rats were given 200, 1000 and 2000 mg/kg 3D185 by single oral gavage. Both male and female animals were well tolerated, and the MTD was greater than 2000 mg/kg.

Beagle dogs were given 50, 250 and 1000 mg/kg 3D185 by single oral gavage and were tolerated by both male and female animals. The main toxicity is mild gastrointestinal symptoms and elevated PHOS. The MTD is greater than 1000 mg/kg.

• Repeat-Dose Toxicity

Sprague Dawley rats were given 3D185 (10, 40 and 120 mg/kg) once a day for 28 days. Male animals in the 120 mg/kg group were intolerant and female animals in each dose group were tolerated. The MTDs of male and female animals were 120 and 40 mg/kg, respectively. The main toxicities are gastrointestinal reactions, bone (sternal and femur) dysplasia, elevated liver function, elevated PHOS, and associated multiple organ mineralization. After 28 days of withdrawal, the above changes were all seen to recover or have a recovery trend. No adverse NOAEL was 10 mg/kg (the plasma AUC_{0-24h} of male and female animals was 2446.4 and 1134.7 ng*h/mL, respectively).

Beagle dogs were given 3D185 (1, 4, and 12/20 mg/kg by oral gavage once a day for 28 consecutive days, including 12 mg/kg for Day 1~20 and 20 mg/kg for Day 21~28 in high dose group). All groups of animals were tolerated. The MTD was > 12 mg/kg. The main toxicities were abnormal skeletal plate development, atrophy of the esophageal mucosa epithelium, and elevated PHOS in some animals. At this dose, the exposure of 3D185 in male and female animals (AUC_{0-24h}) was 9500 and 9260 ng*h/mL, respectively. After 28 days of withdrawal, these changes were seen to recover or have a recovery trend.

2.3. Benefit-risk assessment

3D185 is a highly potent and highly selective FGFR1-3 inhibitor. Since this novel drug is still in the initial stage of clinical development, the available safety and efficacy data mainly comes from preclinical data, and clinical research results of similar drugs. The clinical experience of 3D185 still needs further accumulation.

To date, most of the significant AEs associated with similar drugs that have been observed in the clinical studies are mild to moderate and reversible, such as hyperphosphatemia, nail and mucosal disorders, fatigue, reversible retinal pigment epithelial detachment (RPED), elevated transaminases, hypercalcemia, dyspnea, etc^[10-17]. It was reported that the ORR of FGFR inhibitors in subjects with solid tumors (screened or unscreened) was at the range of 0% to 37.5%, and the DCR was at the range of 22.2% to 91.3%. (Table 1 and Table 2)

NCT	Phases	Drugs	Tumor Types	Results
NCT01212107	Phase 1	LY2874455	Gastric Cancer & NSCLC (no selected)	Gastric cancer (n=29), no ORR; NSCLC (n=24), no ORR.
NCT01703481	Phase 1	JNJ-42756493	Urothelial cancer and other cancers	23 evaluable cases, ORR: 21.7%; DCR: 91.3% (4 PR and 1 unconfirmed PR; 16 SD).
NCT01703481	Phase 1	JNJ-42756493	Cholangiocarcinoma	n=11; ORR: 27.3%; DCR: 54.5%.
NCT02365597	Phase 2	JNJ-42756493	Urothelial cancer	N=87; ORR=32.3%; DCR=78.2%
NCT02393248	Phase 1/2	INCB054828	Cholangiocarcinoma and other cancers	n=49 (part 1, n=22; part 2, n=27). Part 2 ORR: 11%; DCR :37%。
NCT01948297	Phase 1	Debio 1347	Solid tumors	n=57. PR: 6 (8.45%); SD: 16 (28.07%)
			Squamous Lung Cancer	n=36. PR: 11.1%; DCR: 50%
NCT01004224	Phase 1	BGJ398	Bladder/urothelial cancer	n=8. PR: 37.5%; DCR: 75%
			Breast cancer	n=32; SD: 31%
NCT02150967	Phase 2	BGJ398	Cholangiocarcinoma	N=61. ORR: 14.8%; DCR: 75.4%
NCT01976741	Phase 1	BAY 1163877	Bladder/urothelial cancer	n=8; PR: 37.5% (2 FGFR3 mutation or fusion, 1 wild type)
NCT01752920	Phase 1/2	ARQ 087	Cholangiocarcinoma	n=35. PR: 17%; SD: 63%
NCT00979134	Phase 1	AZD4547	Squamous cell carcinoma	n=13. PR: 7.7%; SD: 38.5%
NCT00979134	Phase 1	AZD4547	Gastric cancer	n=13. PR: 7.7%; SD: 30.8%
NCT01795768	Phase 2	AZD4547	Esophageal cancer	n=9 (FGFR2); PR: 33.3%; SD: 22.2%
			Breast cancer	n=8 (FGFR1); PR: 12.5%; SD: 25%
NCT02965378	Phase 2/3	AZD4547	Squamous cell carcinoma	n=27. PR: 8% (4% unconfirmed); SD 48%.

Table 1 Anti-Tumor Activity of Different FGFR Inhibitors

Indications	Types (Frequency)	Drugs	NCT	ORR	SD
	FGFR1	AZD4547	NCT00979134	7.7%	38.5%
	amplification (~10%);	ALD4347	NCT02965378	8%	48%
NSCLC Squamous Lung Cancer	FGFR3 amplification (~1%); FGFR3 fusion (~0.5%); FGFR3mutation (~1%)	BGJ398	NCT01004224	11.1%	38.9%
Devert Commen	FGFR1	AZD4547	NCT01795768	12.5%	25%
Breast Cancer	amplification (~18%)	BGJ398	NCT01004224	0	31%
		BGJ398	NCT01004224	37.5%	37.5%
Metastatic Urothelial	FGFR3 mutation (~20%); FGFR3 amplification (~2%)	BAY 1163877	NCT01976741	37.5%	Undisclosed
Cancer		JNJ-42756493*	NCT01703481	21.7%	69.6%
	(~2/0)	JNJ-42756493	NCT02365597	32.2%	46%
Gastric	FGFR2	A 7D 45 47	NCT00979134	7.7%	30.8%
Cancer/Gastroesophageal Junction Cancer	amplification (10-20%)	AZD4547	NCT01795768	33.3%	22.2%
		ARQ 087	NCT01752920	17%	63%
Chalanaiaaanainama	FGFR2 fusion (10-20%)	BGJ398	NCT02150967	14.8%	60.6%
Cholangiocarcinoma	FGFR2 mutation (<10%)	INCB054828*	NCT02393248	11%	26%
		JNJ-42756493	NCT01703481	27.3%	27.3%
Multi-cancers	/	Debio 1347	NCT01948297	8.5%	28.1%

Table 2Anti-Tumor Activity of Different FGFR Inhibitors in Subjects with SelectiveSolid Tumors

In conclusion, extensive clinical research with selective FGFR inhibitors have demonstrated promising clinical activity in FGFR driven solid tumors with a well characterized and manageable safety profile. Owing to its high selectivity for FGFR1-3, 3D185 has the potential advantage in avoiding the potential toxicity of multi-target inhibition, selecting subjects based on FGFR alterations, and, and enabling rational combination therapy. 3D185 has the potential to become a new and effective drug for cancer subjects.

3. STUDY OBJECTIVES

3.1. Primary Objectives

- a. To assess the safety and tolerability of 3D185 monotherapy in subjects with advanced solid tumors;
- b. To explore the MTD and the RPTD of 3D185 monotherapy in subjects with advanced solid tumors.

3.2. Secondary Objectives

- c. To preliminarily characterize the PK and the PD profiles of single and multiple-dose of 3D185 monotherapy in subjects with advanced solid tumors;
- d. To preliminarily evaluate the anti-tumor activity of 3D185 monotherapy in subjects with advanced solid tumors.

3.3. Exploratory Objective:

e. To explore the relationship between the anti-tumor activity of 3D185 monotherapy and the FGFR alterations in subjects with advanced solid tumors.

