4. STUDY DESIGN AND PLAN

4.1. Overall Plan

This is an open-label, global multicenter, dose-escalation phase 1 study of 3D185 monotherapy in subjects with advanced solid tumors.

The starting dose in this dose-escalation study is 25 mg, and the preset 7 dose-escalation cohorts are 25 mg, 50 mg, 100 mg, 150 mg, 200 mg, 250 mg, and 300 mg, respectively. This study adopts a combination of accelerated titration and i3+3^[1] for dose escalation. All subjects in each cohort will receive a single oral dose of 3D185, followed by a 7-day washout period (i.e. single-dose PK study period). Then, subjects will receive consecutive daily doses (QD, 28 days/cycle) until disease progression, death, unacceptable toxicity, or withdraw of informed consent, whichever comes first. The DLT evaluation period includes the single-dose PK study period and the first treatment cycle (within 35 days after the first dose). The enrolled subjects will be sequentially assigned to the planned dose cohorts according to the protocol, and receive 3D185 treatment to observe the occurrence of DLT:

Accelerated titration dose-escalation phase: One subject is to be enrolled sequentially to 25 mg and 50 mg cohorts, respectively. If no Grade ≥ 2 drug-related AE occurs during DLT evaluation period, the study will escalate to the next dose level. Otherwise, 2 additional subjects will be enrolled, and the subsequent study will convert to i3+3 dose-escalation design from this dose cohort.

In the accelerated titration phase, a subject may be replaced if he/she 1) does not reach to 75% of the total planned dose; 2) discontinued investigational product due to non-DLT reasons during the DLT evaluation period.

i3+3 dose-escalation phase: Starting at 100 mg cohort, 3 subjects are to be enrolled initially at each subsequent dose cohorts in accordance to i3+3 dose-escalation design. Each dose cohort should recruit at least one subject from each country after sites in both countries are activated. If a cohort requires ≥ 6 subjects, it must enroll at least 1 subject from each country and efforts will be made to ensure number of subjects enrolled from each country is similar.

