- 4. CBC with differential: whole blood count (absolute value) includes red blood cell count, white blood cell counts, and differential counts (neutrophils, lymphocytes, monocytes, eosinophils, and basophils), platelet count, hemoglobin, and hematocrit. This test should be completed within 7 days prior to the first dose. It is unnecessary to repeat on C0D1 if the subject has no clinical signs and indications. This test should be completed before dosing within 3 days prior to days C1D1, C1D8, C1D15, C1D28, C2D15, C2D28, CxD28, and safety follow-up period. An unscheduled exam can be performed if there are clinical indications.
- 5. Blood biochemistry includes ALT, AST, total bilirubin, BUN (urea nitrogen) or urea, Cr (creatinine), blood glucose, potassium, sodium, chlorine, calcium, phosphate, magnesium, total protein, albumin, albumin/globulin ratio, LDH (lactate dehydrogenase), and ALP (alkaline phosphatase). This test should be completed within 7 days prior to the first dose. It isn't required to repeat on C0D1 if the subject has no clinical signs and indications. This test should be completed before dosing within 3 days prior to days C1D1, C1D8, C1D15, C1D28, C2D15, C2D28, CxD28 and safety follow-up period. Among them, phosphate levels will also be used for PD analysis.
- 6. Coagulation functions include prothrombin time (PT), APTT, and INR. This test should be completed within 7 days prior to the first dose. It isn't required on C0D1 if the subject has no clinical signs and indications. This test should be completed before dosing within 3 days prior to C1D28, every 8 weeks (±7 days) in additional cycles, and safety follow up visit.

- 7. Urinalysis includes specific gravity, pH, white blood cells, red blood cells, proteins, glucose, ketones, and casts. This exam should be completed within 7 days prior to the first dose. If urine protein ++, it is recommended to test 24-hour urine protein quantitation as soon as possible (if within 72 hours). It isn't required on C0D1 if the subject has no clinical signs and indications. This test should be completed before dosing within 3 days prior to days C1D1, C1D8, C1D15, C1D28, C2D15, C2D28, CxD28, and safety follow-up period.

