7.3. Treatment Period Evaluation Indicators

7.3.1. Single Dose PK Study Period

Day 1 (C0D1)

- PK blood sample collection: within 1 h before dosing and 0.5 h (± 5 min), 1 h (± 5 min), 2 h (±5 min), 3 h (±5 min), 4 h (±5 min), 6 h (±5 min), 8 h (±5 min), and 12 h (± 5 min) after dosing;
- Record the concomitant medications;
- AE collection;
- 12-lead ECG (2 h [±5 min] after dosing).

Day 2 (C0D2)

- PK blood sample collection: 24 h (±5 min) after dosing;
- Record the concomitant medications;
- AE collection.

Day 3 (C0D3)

- PK blood sample collection: 48 h (±10 min) after dosing;
- Record the concomitant medications;
- Adverse event collection.

Day 4 (C0D4)

- PK blood sample collection: 72 h (± 10 min) after dosing;
- Record the concomitant medications;
- AE collection.

Day 5 (C0D5)

- PK blood sample collection: 96 h ($\pm 10 \text{ min}$) after dosing;
- Record the concomitant medications;
- AE collection.

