7.4.4. Pharmacodynamic Assessment

Pharmacodynamic effect may be assessed by analyzing the change in serum phosphate levels relative to baseline level over time (Serum biochemistry test).

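### The protocol promises a single-dose PD profile but schedules only one late serum phosphate (about 96–168 h after the dose) before daily dosing starts

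*Protocol*

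**What the plan says.** **Objective.** Section 3.2, like the synopsis, undertakes to characterise preliminarily the PK and "the PD profiles of single and multiple-dose of 3D185 monotherapy".

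**Measure.** Section 7.4.4 names one PD assessment: "analyzing the change in serum phosphate levels relative to baseline level over time". The synopsis lists the same endpoint. Note 5 to Table 3 gives the source, the routine serum chemistry panel: "Among them, phosphate levels will also be used for PD analysis".

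**Schedule.** Each subject takes one dose on C0D1, "followed by a 7-day washout period (i.e. single-dose PK study period"), and then starts daily dosing on C1D1. For chemistry, note 5 requires a test within 7 days before the first dose. About C0D1 it says "It isn't required to repeat on C0D1 if the subject has no clinical signs and indications". The next required tests are pre-dose at C1D1, C1D8, C1D15 and C1D28, then in later cycles. Section 7.3.2 gives C1D1 a window of -3/+0 days.

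**Visits in between.** In Table 3 the chemistry row is empty from C0D1 to C0D5. Section 7.3.1 lists PK blood, concomitant medications and AEs on those days, plus an ECG on C0D1. Blood is drawn on each of them, for example "PK blood sample collection: 24 h (±5 min) after dosing" on C0D2 and "PK blood sample collection: 48 h (±10 min) after dosing" on C0D3, with further draws at 72 and 96 h.

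**The concern.** A profile over time needs several measurements across the interval in which the marker may move. The protocol provides this for PK after the single dose but not for PD. The schedule is fixed in the protocol, and no later analysis document can supply samples that were never drawn.

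The protocol gives some reason to look early. Section 2.2.1.3 reports raised phosphate among the main findings after single doses in dogs, though at 50–1000 mg/kg. In Section 2.2.1.2, pathway inhibition after a single dose in tumour-bearing mice had almost fully reversed after 6 h at the low dose and 24 h at the high dose.

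At stake is one part of a secondary objective. There is also a reporting risk. Under Section 9.2.1 a subject enters the PD set with a single post-dose phosphate, so the lone C1D1 value would count as PD data and the gap would not be visible in the set's size.

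**Working it through.** The plan gives no figure to reproduce. The check counts scheduled samples and then places the one available sample in time.

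**1. Sample count after the single dose and before daily dosing** (Table 3, notes 5 and 15, Sections 7.3.1 and 7.3.2)

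| | C0D1 post-dose to C0D5 | Pre-dose C1D1 chemistry |
|---|---|---|
| PK | 12 times (0.5, 1, 2, 3, 4, 6, 8, 12, 24, 48, 72, 96 h) | – |
| Serum phosphate | 0 | 1 |

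**2. Timing of the one phosphate value.** The single-dose period is Days 1–7, so C1D1 is Day 8:

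- nominal time: 7 × 24 = 168 h after the dose;
- early edge of the window: (7 − 3) × 24 = 96 h.

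The time can therefore differ by up to 72 h between subjects.

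**3. What one value can give.** It yields one change from the screening baseline. A peak, a time to peak or a time course needs more than one post-dose time, and this holds whatever the kinetics are.

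**4. How late 96–168 h may be.** The only kinetic figures are animal plasma half-lives in Section 2.2.1.1: 6.78 h in rats and 12.8 h in dogs. No human value is given, so 24 h and 48 h are assumptions to show a range. The number of half-lives is t / t½, and the fraction of drug left is 2^(−t / t½).

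| t½ | at 96 h | at 168 h |
|---|---|---|
| 6.78 h (rat) | 14.2 half-lives, under 0.01% left | 24.8 half-lives, under 0.01% left |
| 12.8 h (dog) | 7.5 half-lives, 0.55% left | 13.1 half-lives, 0.01% left |
| 24 h (assumed) | 4.0 half-lives, 6.3% left | 7.0 half-lives, 0.8% left |
| 48 h (assumed) | 2.0 half-lives, 25% left | 3.5 half-lives, 8.8% left |

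These are fractions of drug, not of phosphate response. They show that the sample may come after most of the drug has gone, not that the phosphate effect has.

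**5. Multiple-dose part.** Phosphate is scheduled at C1D8, C1D15, C1D28, C2D15, C2D28 and in later cycles, so this part of the objective is served.

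**The case against.** **The effect may outlast the drug.** This stands. Drug half-life is only a proxy for phosphate kinetics. The protocol's own rules allow for slow recovery: the DLT definition gives 14 days for phosphorus to fall below 7 mg/dL, and Table 4 provides for a return to below 5.5 mg/dL taking 7–28 days. Those rules concern marked elevations under treatment, so they do not show persistence after one dose. They do rule out treating the half-life arithmetic as proof. A reader might infer that the single-dose result will show no effect whatever the truth; the documents do not support that, because a slow or lasting rise could still be seen at C1D1.

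**A post-dose value does exist.** This also stands. It is wrong to say that there is no phosphate after the single dose; there is one, late. Clinically indicated unscheduled tests (Section 7.4.1.2) could add values, but only in selected subjects.

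**The objective is preliminary and may be loosely worded.** One phrase covers PK and PD, single and multiple dose, and the interval is named a PK period. That may explain the mismatch but does not remove it, since the objective names single-dose PD. If it was not intended, the wording should change.

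**The recommended dose does not depend on it.** A reader might infer that data needed for the recommended dose are lost. The documents do not support this. Section 4.1 bases that dose on PK and/or PD profiles together with safety data, and no passage requires single-dose PD. Phosphate under daily dosing is well sampled.

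**The remedy is not free.** PK samples go to a central laboratory (Section 7.4.3) and safety chemistry is local (Section 7.4.1.2), so the PK tube will not serve. Subjects also restrict phosphate intake to 600–800 mg/day during treatment, including the DLT period (Section 6.3.1). An early change from a pre-treatment baseline may therefore mix diet and drug.

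**Conclusion.** The objective and the schedule do not match. The single-dose PD profile cannot be characterised from one phosphate value taken about 96–168 h after the dose. This rests on the protocol's schedule alone, not on any assumption about half-life.

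The size of the loss is uncertain. If phosphate follows the drug with a half-life like the dog's, the sample falls 7.5–13.1 half-lives after the dose and would probably show only a return to baseline. With an assumed human half-life of 24–48 h it falls at 2–7 half-lives and could show a residual change.

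The finding goes no further. It does not show that a single-dose effect would go undetected, nor that dose selection is compromised. The primary safety and MTD objectives and multiple-dose PD are untouched. The point is still worth correcting, because a stated secondary objective lacks the data it needs and the remedy is small.

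**What to change.** Choose one of two changes.

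**Add samples.** Schedule a serum phosphate at the existing 24, 48, 72 and 96 h PK draws (C0D2–C0D5), in Section 7.3.1, Table 3 and note 5. Specify a separate tube for the local laboratory at the same venepuncture. With C1D1 this gives 4 + 1 = 5 post-single-dose values instead of one; if the C1D1 chemistry is drawn at the 96 h edge, two of the five fall at about the same time. The grid resolves the course to about a day, so a change confined to the first 24 h would still be missed.

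**Or narrow the objective.** Limit the PD part of Section 3.2 and the synopsis to multiple dosing, leaving single-dose PK as it is. This costs only wording.

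The first option costs up to four extra tubes and local assays per subject, or 4 × 42 = 168 at the expected maximum of 42 subjects, with no extra visit or needle stick. State with the result that early change from the screening baseline may partly reflect the phosphate-restricted diet.
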